## Schema

### Figure 1      Study Design

#### Study Design

#### Study Schedule

†All visits include blood and urine collection as well as safety assessments.

CV = cardiovascular; eGFR = estimated glomerular filtration rate; LDL-C = low density lipoprotein cholesterol; MAD = multiple ascending dose.

## 1.2      Schedule of Activities

The Schedule of Activities (SoA) is provided in [Table 1](#).

**Table 1** Schedule of Activities

	Screening	Treatment period							Final follow-up/EDV
Visit number	1	2	3	4	5	6	7	8	
Study day	D -21 to D -1	D1	D8	D15	D29	D57	D85	D99	
Visit window			± 3 days						
Informed consent	X								
Inclusion/exclusion criteria	X	X							
Demographic data	X								
Medical history	X								
Height, weight, and BMI (height at screening only)	X	X	X	X	X	X	X	X	
Drugs of abuse screening a	X								
Urine pregnancy test (local) b	X	X							
FSH	X								
LH	X								
HbA1c	X							X	
Serology	X								
COVID-19 test c	X	X							
Concomitant medication review	X	X	X	X	X	X	X	X	
Dispensing of AZD0780/Placebo (35 tablets per bottle)		X			X	X			
Study intervention administration (AZD0780/Placebo)		X (Once daily oral dosing; Day 1 through Day 84)							

**Table 1** Schedule of Activities

	Screening	Treatment period						Final follow-up/EDV
Visit number	1	2	3	4	5	6	7	8
Study day	D -21 to D -1	D1	D8	D15	D29	D57	D85	D99
Visit window			± 3 days					
Safety and Tolerability								
Adverse event review	X (SAEs only)	X (AEs as of dosing)	X	X	X	X	X	X
Physical examination (full)	X	X						X
Physical examination (brief)			X	X	X	X	X	
Vital signs (BP, pulse and temperature, respiratory rate, pulse oximetry) d	X	X	X	X	X	X	X	X
12-lead safety ECG e	X	X	X	X	X	X	X	X
Clinical safety laboratory evaluations (chemistry, hematology, coagulation, urinalysis)	X	X	X	X	X	X	X	X
Urine renal safety biomarkers: albumin, creatinine, total protein	X	X	X	X	X	X	X	X
Efficacy/Pharmacokinetics/Pharmacodynamics (fasted)f								
Lipid profile (TC, HDL-C, non-HDL-C, triglycerides)	X	X	X	X	X	X	X	X
LDL-C	X	X	X	X	X	X	X	X
ApoB		X	X	X	X	X	X	X

**Table 1** Schedule of Activities

	Screening	Treatment period							Final follow-up/EDV
Visit number	1	2	3	4	5	6	7	8	
Study day	D -21 to D -1	D1	D8	D15	D29	D57	D85	D99	
Visit window			± 3 days						
ApoA1		X			X	X	X	X	
Lp(a)		X			X	X	X	X	
hsCRP		X			X	X	X	X	
PK plasma samples f			X	X	X	X	X		
Exploratory									
Blood sample for total PCSK9		X							
Blood (serum) sample for biomarker analyses		X			X	X	X	X	
Blood (plasma) sample for biomarker analyses		X			X	X	X	X	
Urine sample for biomarker analyses		X			X	X	X	X	
Sample for Genomic Initiative (optional) g		X							

a Screening for drugs of abuse may be performed as per guidelines at local site.

b Eligibility is confirmed by negative urine pregnancy test. Confirmatory serum test analyzed at the central laboratory is indicated if urine test is positive at Visit 1.

c COVID-19 tests will be performed as per investigator's discretion and according to the study centers' local procedures.

d Three consecutive BP and pulse readings should be recorded at intervals of at least 2 minutes.

e 12-lead ECGs should be obtained in triplicate.

f Blood samples must be obtained pre-dose of IMP for each applicable visit.

g Consent and sample collection for genetic testing will only be conducted in countries where genetic testing is allowed in this study. If sample is not collected at Visit 2, it can be collected at any subsequent visit until the last study visit; to be collected per local guidelines.

Participants are required to fast for at least 8 hours overnight prior to all study visits (including screening). Participants are permitted to drink water during this period of fasting until 1 hour before blood sampling.

AE = adverse event; ApoA1 = apolipoprotein A-1; ApoB = apolipoprotein B-100; BMI = body mass index; BP = blood pressure; COVID-19 = Coronavirus disease 2019; ECG = electrocardiogram; EDV = early discontinuation visit; FSH = follicle stimulating hormone; HbA1c = hemoglobin A1c; HDL-C = high-density lipoprotein cholesterol; hsCRP = high-sensitivity C-reactive protein; IMP = investigational medicinal product; LDL-C = low-density lipoprotein cholesterol; LH = luteinizing hormone; Lp(a) = lipoprotein (a); PCSK9 = proprotein convertase subtilisin/kexin type 9; PK = pharmacokinetic(s); SAE = serious adverse event; TC = total cholesterol.

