## 4 STUDY DESIGN

### 4.1 Overall Design

This is a randomized, multicenter, parallel-group, double-blind, placebo-controlled, dose-ranging, Phase IIb study in approximately 375 participants with dyslipidemia. The primary objective of the study is to investigate the effect of AZD0780 on LDL-C levels across different dose levels. An overview of the study design is provided in [Figure 1](#). The study will be conducted at up to 65 sites in up to 8 countries.

The study population will consist of male and female participants of non-childbearing potential, 18 to 75 years of age with a fasting LDL-C of  $\geq 70$  (1.8 mmol/L) and  $< 190$  mg/dL (4.9 mmol/L) at screening.

The screening period will be up to 3 weeks prior to randomization, ie, participants will be randomized at any time between Day -21 and Day -1 providing all eligibility criteria have been met. Participants with a fasting LDL-C of  $\geq 70$  mg/dL and  $< 190$  mg/dL, and triglycerides  $< 400$  mg/dL at screening will be eligible. Participants will also be receiving moderate or high-intensity statin therapy for at least 2 months prior to screening (please refer to [Appendix F](#)). Eligible participants will attend 6 visits during the treatment period and one additional visit in the follow-up period. Eligible participants will be randomized across 5 different treatment arms in a 1:1:1:1:1 ratio for a 12-week treatment period. The planned treatments arms are AZD0780 [REDACTED] mg, AZD0780 [REDACTED] mg, AZD0780 [REDACTED] mg, AZD0780 [REDACTED] mg, and placebo.

Blood samples will be collected for analysis of LDL-C (Friedewald calculation + reflex testing for triglycerides  $> 400$  mg/dL and/or LDL-C  $< 40$  mg/dL) will be obtained to assess the effects of AZD0780 on these parameters. Blood samples for analysis of lipid profile (total cholesterol, HDL-C, triglycerides, ApoB, Lp(a), ApoA1) will be obtained to assess the effects of AZD0780 on these parameters. Samples will be collected, labeled, stored and shipped as detailed in the Laboratory Manual.

The study is double-blind and AZD0780 and placebo will be matched for appearance. Participants will begin treatment (placebo or AZD0780) on Day 1 and continue for 12 weeks. After the treatment period, participants will have one follow-up visit 2 weeks post last dose. For detailed information, please refer to the SoA ([Table 1](#)).

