## **8 STUDY ASSESSMENTS AND PROCEDURES**

- Study procedures and their timing are summarized in the SoA (Section 1.2). Protocol waivers or exemptions are not allowed.
- Urgent safety concerns should be discussed with the investigator upon occurrence or awareness to determine if the participant should continue or discontinue study intervention.
- Adherence to the study design requirements, including those specified in the SoA, is essential and required for study conduct.
- All screening evaluations must be completed and reviewed to confirm that potential participants meet all eligibility criteria. The investigator will maintain a screening log to record details of all participants screened and to confirm eligibility or record reasons for screening failure, as applicable.
- Procedures conducted as part of the participant's routine clinical management (eg, blood count) and obtained before signing of the ICF may be utilized for screening or baseline purposes provided the procedures met the protocol-specified criteria and were performed within the time frame defined in the SoA.
- Instructions for the collection and handling of HBS will be provided in the study-specific laboratory manual. Samples should be stored in a secure storage space with adequate measures to protect confidentiality. For further details on handling of HBS see [Appendix C](#).

In the event of a significant study-continuity issue (eg, caused by a pandemic), alternate strategies for participant visits, assessments, medication distribution and monitoring may be implemented by the Sponsor or the investigator, as per local health authority/ethics requirements.

Laboratory and analyte results that could unblind the study will not be reported to investigative sites or other blinded personnel until the study has been unblinded.

The approximate amount of blood collected from each participant over the duration of the study is around 300ml (approximately 20 tablespoons), and the maximum amount of blood collected from each participant over the duration of the study, including any extra assessments that may be required, will not exceed 500 mL (approximately 33 tablespoons). Repeat or unscheduled samples may be taken for safety reasons or for technical issues with the samples.

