## 8.4 Pharmacokinetics

### 8.4.1 Collection of Samples for Pharmacokinetics

Blood samples will be collected for measurement of plasma concentrations of AZD0780 as specified in the SoA (Section 1.2). On days where PK samples are to be collected the patient should refrain from taking the study medication prior to coming to the clinic. The PK samples are to be collected prior to administering the study medication at the clinic.

Plasma concentrations will be summarized by treatment (dose level of AZD0780) for each sampling time point, using descriptive statistics based on the PK analysis set and included in the CSR.

Samples will be collected, labeled, stored, and shipped as detailed in the Laboratory Manual.

PK data from this study, possibly together with data from other studies, may be used for population PK/PD analysis. The results of any such modeling activity will be provided in a separate report (as an appendix to the CSR or as a stand-alone report).

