3.3.1.4 Intercurrent Events

Intercurrent events (ICEs) are events that happen after treatment initiation and affect either the existence or interpretation of planned measurements.

The intercurrent events, and the applied analysis strategy considered in this SAP are summarized in Table 3.

Table 3– Expected ICEs and the Corresponding Statistical Considerations by Estimand

ICEs	Hypothetical strategy for ICEs defined in the CSP	Treatment policy strategy for ICEs defined in the CSP	Handling in the safety analysis	
			On-treatment	On-study
1. Premature and permanent discontinuation of study treatment	Hypothetical strategy	Treatment policy strategy	Hypothetical strategy	Treatment policy strategy
2. Change in background lipid lowering statin therapy	Hypothetical strategy	Treatment policy strategy	Treatment policy strategy	
3. Initiation, change or discontinuation in non-prohibited background lipid lowering non-statin therapy	Hypothetical strategy	Treatment policy strategy	Treatment policy strategy	
4. (a) Prohibited medication affecting lipid parameters	Hypothetical strategy	Treatment policy strategy	Treatment policy strategy	
(b) Prohibited medication not affecting lipid parameters	Treatment policy strategy		Treatment policy strategy	
5. Any concomitant medication not explicitly specified in the above categories	Treatment policy strategy		Treatment policy strategy	

6. Death	Hypothetical strategy	Hypothetical strategy	Hypothetical strategy	Hypothetical strategy
----------	-----------------------	-----------------------	-----------------------	-----------------------

ICEs – Intercurrent Events

The occurrence of any ICE does not automatically trigger premature and permanent study discontinuation as described in Section 7. of the latest approved CSP. In case of still applying consent, the participants are expected to attend assessments as described in the Schedule of Activities.

The following ICEs are considered:

1 Premature and permanent discontinuation of study treatment

2 Change in background lipid lowering statin therapy

The allowed background lipid lowering statin therapies are described in Appendix F of the last approved version of CSP and the latest approved version of the Statin eligibility memo. Background therapy is recorded in the EDC as prior medication.

Possible mechanisms of change in background lipid lowering statin therapy include:

(a) Discontinue statin therapy

(b) Change to a different statin therapy in the same intensity category

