4.2.1 Primary Endpoint

4.2.1.1 Definition

The primary efficacy endpoint is percent change from baseline to Week 12 in direct LDL-C. The clinical question of interest is:

What is the difference in means of percent change in LDL-C from baseline to Week 12 in participants with dyslipidemia treated with AZD0780 vs placebo in the hypothetical condition that all participants could adhere to study intervention and non-prohibited

background lipid lowering statin and non-statin therapy, prohibited medications affecting lipid parameters were not available, regardless of whether additional treatment is used, where participants cannot die.

The primary estimand attributes are defined as:

- Treatment: AZD0780 or placebo.
- Population: Male and female participants of non-childbearing potential, 18 to 75 years of age with dyslipidemia, defined by the inclusion and exclusion criteria. Implemented using FAS.
- Endpoint: Percent change in direct LDL-C from baseline at Week 12.
- Population-level summary measure: Difference in means of percent change in direct LDL-C from baseline to Week 12 between AZD0780 and placebo.
- Handling of intercurrent event: The hypothetical strategy will be used for premature and permanent discontinuation of study treatment; change in background lipid lowering statin therapy; initiation, change or discontinuation in non-prohibited background lipid lowering non-statin therapy and intake of prohibited medications affecting lipid parameters. Efficacy assessments obtained after these will not be included in the analysis. Initiation or changes in other concomitant or prohibited medication will be handled with treatment policy strategy. Deaths will be handled with a hypothetical strategy.

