4.2.1.2 Derivations

Direct LDL-C below the LLOQ for which the exact value cannot be determined, will be replaced with the LLOQ divided by the squared root of 2.

Percent change from baseline is derived as:

$$\frac{(y_{V_j} - y_{BL})}{y_{BL}} * 100$$

where

- y_{V_j} represents the efficacy measurement at Visit j , and
 - j refers to the visit number, specifically 3,4,5,6,7 (i.e., the visits included in the analysis),
 - In case of treatment discontinuation ICE, j includes all visits up to and including the date of treatment discontinuation.

- For every other ICE handled with the hypothetical strategy, j refers to the last visit before the first ICE occurrence handled with the hypothetical strategy, as detailed in Section 3.3.1.4.
- y_{BL} is the efficacy measurement at Baseline.

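### The Schedule of Activities ends dosing on Day 84 although Visit 7 can fall as late as Day 88, and Section 8.4.1 implies a dose is still due there, so some Week 12 LDL-C samples may be taken 2 to 4 days off drug

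*Protocol*

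**What the plan says.** **Dosing and visit days.** Protocol Section 1.2 (Table 1) gives study intervention as "Once daily oral dosing; Day 1 through Day 84". Visit 7 is on Day 85 and carries the Week 12 LDL-C and the last PK sample. The ±3-day visit window is extracted as a single table cell; I read it as covering Visit 7. Section 8 makes the schedule binding: "Adherence to the study design requirements, including those specified in the SoA, is essential and required for study conduct".

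**Text pointing to a dose at Visit 7.** Section 8.4.1 tells participants not to take study drug before coming in on PK days, and adds: "The PK samples are to be collected prior to administering the study medication at the clinic". Section 4.1 says "participants will have one follow-up visit 2 weeks post last dose", and the SoA places that visit on Day 99.

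**What the SAP does with the sample.** SAP Table 5 maps Days 80 to 90 to Week 12. The discontinuation intercurrent event in SAP 3.3.1.4 is limited to "Premature and permanent discontinuation of study treatment". SAP 4.1.1.1 counts anyone who has not stopped prematurely as having completed treatment.

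**The concern.** On the nominal calendar the plan is coherent: the last dose is on Day 84 and the sample on Day 85, one day later. The difficulty arises only when Visit 7 is late. The SoA then gives an explicit last dosing day, while Section 8.4.1 assumes a clinic dose on the visit day. Nothing says which prevails, and sites may resolve it differently.

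At sites that follow the SoA, late participants in the active arms would be measured while the LDL-C effect may already be fading, and only at the primary timepoint. The primary question in SAP 4.2.1.1 is framed "in the hypothetical condition that all participants could adhere to study intervention". A reader would take the Week 12 estimate as the effect under continuing daily dosing. The trial is meant to guide the choice of doses and sample sizes (Protocol Section 2.1), so the size of that estimate matters as well as its significance.

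**Working it through.** **Inputs.** Last dosing day 84, Visit 7 target Day 85 and window ±3 days (Protocol Table 1); Week 12 analysis window Days 80–90 (SAP Table 5); on-treatment period to last dose + 10 days (SAP 3.3.1.3).

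**1. The plan's own figure.** A 12-week course is 12 × 7 = 84 days, and Day 1 through Day 84 is 84 − 1 + 1 = 84 days. The two agree.

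**2. Visit 7 window.** 85 − 3 = 82 and 85 + 3 = 88, so Days 82 to 88.

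**3. Time off drug if the SoA is followed.** The sample is taken pre-dose, so on Days 82 to 84 the preceding dose is the day before. From Day 85 it is Day 84.

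| Visit 7 on | Last dose before sample | Days since last dose | Daily doses not taken |
|---|---|---|---|
| D82 | D81 | 1 | 0 |
| D83 | D82 | 1 | 0 |
| D84 | D83 | 1 | 0 |
| D85 | D84 | 1 | 0 |
| D86 | D84 | 2 | 1 |
| D87 | D84 | 3 | 2 |
| D88 | D84 | 4 | 3 |

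Days 86 to 88 are the ones that matter for efficacy. On Day 85 the protocol texts disagree about a clinic dose, but the sample is one day after the last dose either way.

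**4. Does the SAP remove these values?** Days 86 to 88 lie inside Days 80–90. A participant who stops on Day 84 as scheduled has not stopped prematurely, so the discontinuation event does not apply and neither does its cut-off rule in SAP 4.2.1.2. The on-treatment period would run to 84 + 10 = Day 94 and so covers these days, but it serves the safety analyses and the MI-RD imputation status. It does not select values for the primary MMRM. The values therefore stay in.

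**5. Other timepoints.** The latest in-window days for the earlier visits are 8 + 3 = 11, 15 + 3 = 18, 29 + 3 = 32 and 57 + 3 = 60, all within dosing. Only Week 12 is exposed.

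**6. Size.** The dilution of an arm's mean effect is (share of participants seen late) × (mean fraction of effect lost among them). The documents give neither factor. Protocol Section 4.2.4 describes onset (LDL-C steady state within about 2 weeks), not offset, and the assumed difference and SD are redacted. No figure can be derived.

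**The case against.** The strongest reply is that the SoA is a grid of nominal days and the rest of the text leans toward dosing up to the visit. Section 8.4.1 expects a clinic dose on PK days. SAP 3.3.1.5 has participants take one tablet per bottle per day and gives no stop day. The 35-tablet bottles dispensed on Day 57 last to 57 + 35 − 1 = Day 91. A follow-up two weeks after the last dose, at Day 99, implies 99 − 14 = Day 85. All of this stands. It makes the matter an inconsistency with a conditional consequence, because the only explicit end day in the protocol is still Day 84.

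A reader might also infer more than the documents support:

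- **That sites do stop participants on Day 84, or that many visits are late.** Neither is shown.
- **That the SAP is stricter with early stoppers than with completers.** For discontinuation, SAP 4.2.1.2 "includes all visits up to and including the date of treatment discontinuation". The contrast works only if that date means the last-dose date, which is not stated. A completer who took every scheduled dose has also adhered, so keeping the value fits the estimand as written.
- **That SoA footnote f is also in conflict.** It reads "Blood samples must be obtained pre-dose of IMP for each applicable visit", and the last words already allow for a visit without a dose.
- **That the dose-response or power is materially distorted.** Any number would rest on an invented offset rate and share of late visits.

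**Conclusion.** The inconsistency is real and the fix is cheap, but the point is minor. If a site follows the SoA and Visit 7 falls on Day 86, 87 or 88, the primary LDL-C sample and the last PK sample come 2, 3 or 4 days after the last dose, and the LDL-C value enters the primary MMRM. This rests on two conditions: that the 3-day window applies to Visit 7, and that the site takes Day 84 literally.

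Any bias is toward placebo, since only the active arms have an effect to lose. It is limited to late visits, cannot create false efficacy, and has a size that the documents do not allow one to compute. Exposure/response modelling, if performed, is to use off-treatment data (SAP 4.4) and could allow for the gap; the primary MMRM makes no such allowance.

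**What to change.** **If dosing can still be changed:**

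- Change the SoA line to: *once daily from Day 1 through Day 84, or through the day before Visit 7 if Visit 7 is later*. Every in-window Week 12 sample is then one day after the last scheduled dose, and no planned course is shorter than 84 days.
- State in Section 8.4.1 that no clinic dose is given at a Visit 7 on or after Day 85. Footnote f can stay.
- Set Visit 8 at 14 ± 3 days after the last dose, in keeping with Section 4.1. A last dose on Day 84 gives 84 + 11 = D95 to 84 + 17 = D101; on Day 87 it gives 87 + 11 = D98 to 87 + 17 = D104. The overall range D95–D104 lies inside the SAP Week 14 window (D94–D104). The earliest visit, at last dose + 11, always follows the on-treatment period, which ends at last dose + 10. Keeping Day 99 ± 3 would not be clean: after a last dose on Day 87 the on-treatment period runs to Day 97, so a Visit 8 on Day 96 or 97 would count as on-treatment.

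**Supply.** The worst in-window needs per bottle, dosing to the day before the next dispensing visit or Visit 7, are:

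- D1–D31: 31 tablets
- D26–D59: 59 − 26 + 1 = 34 tablets
- D54–D87: 87 − 54 + 1 = 34 tablets

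All are below the 35 dispensed.

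**Cost.** One SoA line, one sentence in Section 8.4.1 and a restated Visit 8. Treatment length varies from 84 to 87 days instead of a fixed 84. The compliance calculation in SAP 4.1.9 uses actual first and last dose dates, so it needs no change.

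**If dosing is already complete:** add one table of days since last dose at the Week 12 LDL-C sample, by arm. Last-dose dates are mandatory eCRF fields (SAP 3.3.1.6), so no new data are needed.

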## 2 INTRODUCTION

### 2.1 Study Rationale

AZD0780 is a small molecule inhibitor of PCSK9 for the reduction of circulating levels of LDL-C. This study aims to evaluate the dose-dependent reduction in LDL-C as well as the associated adverse effects profile after oral administration of multiple doses of AZD0780 on background standard of care therapy including medium to high-intensity statins. The data generated will be used to guide choice of doses, dosing regimens, and sample sizes, as well as safety and PD monitoring in the further clinical development program.

